7.7 Five-year follow up analysis

The change in SER measured by autorefractor will be compared at baseline to five years, as well as from 24 months to five years. If SER is not available at five years, spectacle refraction based on current prescription will be used.

Doc No: ST06-RD01 Page **15** of **47**

[figure not shown]
8. ANALYSIS DETAILS

The results of the analyses will be reported following the principles of the ICH E3 guidelines on the Structure and Content of Clinical Study Reports.

8.1 Recruitment and follow-up patterns

- Screening, patient enrolment, treatment allocation, withdrawals, follow-up and inclusion in primary analysis will be reported using CONSORT diagram.
- Recruitment will be reported by site.

8.2 CONSORT Flow Diagram

Doc No: ST06-RD01 Page **16** of **47**

8.3 Baseline Characteristics

- Minimisation factors, n (%) by treatment arm and total
- Gender, n (%) by treatment arm and total
- Age (years), mean (SD) by treatment arm and total
- Weight (kg), mean (SD) by treatment arm and total
- Height (cm), mean (SD) by treatment arm and total
- Ethnicity, no. (%) by treatment arm and total
- Parental myopia, no. (%) by treatment arm and total
- SER in both eyes, mean (SD) by treatment arm and total
- SER in left eye, mean (SD) by treatment arm and total
- SER in right eye, mean (SD) by treatment arm and total
- Central axial length in both eyes, mean (SD) by treatment arm and total
- Central axial length in left eye, mean (SD) by treatment arm and total
- Central axial length in right eye, mean (SD) by treatment arm and total
- EQ5D-Y- Visual Analogue Scale, mean (SD) by treatment arm and total
- EQ5D-Y- index score, mean (SD) by treatment arm and total
- Uniocular BCdVA in both eyes, mean (SD) by treatment arm and total
- Uniocular BCdVA in left eye, mean (SD) by treatment arm and total
- Uniocular BCdVA in right eye, mean (SD) by treatment arm and total
- Binocular BCdVA, mean (SD) by treatment arm and total
- Uniocular near VA in both eyes, mean (SD) by treatment arm and total
- Uniocular near VA in left eye, mean (SD) by treatment arm and total
- Uniocular near VA in right eye, mean (SD) by treatment arm and total
- Binocular near VA, mean (SD) by treatment arm and total
- · Reading speed, mean (SD) by treatment arm and total
- Pupil diameter in both eyes, mean (SD) by treatment arm and total
- Pupil diameter in left eve. mean (SD) by treatment arm and total
- Pupil diameter in right eye, mean (SD) by treatment arm and total
- Spectacle correction, no. (%) by treatment arm and total
- Frequency of spectacle correction; all day and sometimes, no. (%) by treatment arm and total
- Contact lens use, no. (%) by treatment arm and total
- Frequency of contact lens use; all day and sometimes, no. (%) by treatment arm and total

8.4 Trial treatment

- · Time from randomisation to start of study drug, mean (sd) by treatment arm
- Medical Events Monitoring System (MEMS): Average adherence (%), average drug holidays and average overdosing over total study time period, mean (sd) by treatment arm
- Reasons for termination of study drug: number (%) by treatment arm for study drug related AE, study drug related SAE, study drug expiry date, patient request, clinicians request and other
- Protocol deviations/violations: number (%) by treatment arm for eligibility, study drug administration (participant reported), study drug administration (MEMS data), safety reporting (AE/SAE), visit outside schedule OR missed visit, assessment not done and other
- Premature withdrawals: number (%) by treatment arm for adverse event, serious adverse event, protocol deviation, lost to follow up, withdrawal of patient consent, death, withdrawal at clinician's request and other
- Did not receive allocated treatment (which includes those who received no treatment), number
 (%) by treatment arm
- Received treatment of other group, number (%) by treatment arm

8.5 Trial Outcomes

Primary efficacy outcome:

 SER at month 24: mean (SD) by treatment arm, difference in means with 95% CI, p-value from GEE model, adjusted for baseline SER in ITT analysis and PP analysis.

Secondary analysis of the primary efficacy outcome:

- SER at month 24: mean (SD) by treatment arm, difference in means with 95% CI, p-value from GEE model, adjusted for baseline SER, minimisation variables (i.e. site and ethnicity), baseline age and history of parental myopia (at least one parent), in ITT analysis and PP analysis.
- Uniocular (BCdVA) at month 24: mean (SD) by treatment arm, difference in means with 95% CI, p-value from GEE, adjusted for baseline uniocular BCdVA in ITT and PP analysis.
- Binocular BCdVA at month 24: mean (SD) by treatment arm, difference in means with 95% CI,
 p-value from ANCOVA, adjusted for baseline BCdVA in ITT and PP analysis.
- Central axial length at month 24: mean (SD) by treatment arm, difference in means with 95% CI,
 p-value from GEE, adjusted for baseline central axial length in ITT and PP analysis.
- Uniocular near VA at month 24: mean (SD) by treatment arm, difference in means with 95% CI, p-value from GEE, adjusted for baseline uniocular near VA in ITT and PP analysis.
- Binocular near VA at month 24: mean (SD) by treatment arm, difference in means with 95% CI, p-value from ANCOVA, adjusted for baseline binocular near VA in in ITT and PP analysis..
- Pupil diameter at month 24: mean (SD) by treatment arm, difference in means with 95% CI, p-value from GEE, adjusted for baseline pupil diameter in ITT and PP analysis.
- Spectacle correction at month 24: no. (%) by treatment arm, risk difference and p-value from from chi-square test in ITT and PP analysis.
- Frequency of spectacle correction at month 24 (all day and sometimes): no. (%) by treatment arm in ITT and PP analysis.
- EQ-5D-Y VAS at month 24: mean (SD) by treatment arm, difference in means with 95% CI, p-value from ANCOVA, adjusted for baseline EQ-5D-Y VAS in intention to treat analysis and per protocol analysis.
- EQ-5D-Y Index score at month 24: mean (SD) by treatment arm, difference in means with 95% CI, p-value from ANCOVA, adjusted for baseline EQ-5D-Y index in ITT and PP analysis.
- Tolerability eye feels at month 24: mean (SD) by treatment arm, difference in means with 95% CI, p-value from independent t-test, in ITT and PP analysis.
- Tolerability stingy at month 24: mean (SD) by treatment arm, difference in means with 95% CI, p-value from independent t-test, in ITT and PP analysis.
- Tolerability itchiness at month 24: mean (SD) by treatment arm, difference in means with 95% CI, p-value from independent t-test, in ITT and PP analysis.
- Tolerability blurry vision at month 24: mean (SD) by treatment arm, difference in means with 95% CI, p-value from independent t-test, in ITT and PP analysis.
- Tolerability sore eyes at month 24: mean (SD) by treatment arm, difference in means with 95% CI, p-value from independent t-test, in ITT and PP analysis.
- Tolerability difficult to read/write at month 24: mean (SD) by treatment arm, difference in means with 95% CI, p-value from independent t-test, in ITT and PP analysis.

8.6 Sensitivity analyses

- SER at month 24: mean (SD) by treatment arm, difference in means with 95% CI, p-value from GEE model, adjusted for baseline SER in ITT and PP analysis.
- SER at month 24: mean (SD) by treatment arm, difference in means with 95% CI, p-value from GEE model, adjusted for baseline SER and minimisation variables (i.e. site and ethnicity), baseline age and history of parental myopia (at least one parent), in ITT and PP analysis.

8.7 Subgroup analyses

- SER at month 24 according to age group (6-9 and 10-12): mean (SD) by treatment arm, difference in means with 95% CI, p-value from GEE model, adjusted for baseline SER in ITT and PP analysis.
- SER at month 24 according to ethnicity group (white and non-white): mean (SD) by treatment arm, difference in means with 95% CI, p-value from GEE model, adjusted for baseline SER in ITT and PP analysis.

- SER at month 24 according to severity of myopia (less than -3D and -3D or greater): mean (SD) by treatment arm, difference in means with 95% CI, p-value from GEE model, adjusted for baseline SER in ITT and PP analysis.
- SER at month 24 according to iris colour (Dark brown and Other including; light brown, green, blue and grey): mean (SD) by treatment arm, difference in means with 95% CI, p-value from GEE model, adjusted for baseline SER in ITT and PP analysis.
- SER at month 24 according to gender (male/female): mean (SD) by treatment arm, difference in means with 95% CI, p-value from GEE model, adjusted for baseline SER in ITT and PP analysis.

8.8 Additional analyses

Primary outcome:

- SER at baseline, mean (SD) by treatment arm in PP analysis.
- SER at months 6, 12 and 18, mean (SD) by treatment arm, difference in means with 95% CI, p-value from GEE (repeated measures model), adjusted for baseline SER, in ITT and PP analysis.
- SER at months 6, 12 and 18, mean (SD) by treatment arm, difference in means with 95% CI, p-value from GEE (repeated measures model), adjusted for baseline SER, minimisation variables (i.e. site and ethnicity), baseline age and history of parental myopia, in ITT analysis and PP analysis.

Secondary outcomes:

- Reading speed at baseline, mean (SD) by treatment arm in PP analysis.
- Reading speed at months 6, 12 and 18: mean (SD) by treatment arm, difference in means with 95% CI, p-value from repeated measures ANCOVA, adjusted for baseline reading speed in ITT and PP analysis.
- Uniocular BCdVA at baseline, mean (SD) by treatment arm in PP analysis.
- Uniocular BCdVA at months 6, 12 and 18: mean (SD) by treatment arm, difference in means with 95% CI, p-value from GEE (repeated measures model), adjusted for baseline uniocular BCdVA in ITT and PP analysis.
- Binocular BCdVA at baseline, mean (SD) by treatment arm in PP analysis.
- Binocular BCdVA at months 6, 12 and 18: mean (SD) by treatment arm, difference in means with 95% CI, p-value from repeated measures ANCOVA, adjusted for baseline BCdVA in ITT and PP analysis.
- Central axial length at baseline, mean (SD) by treatment arm in PP analysis.
- Central axial length at months 6, 12 and 18 mean (SD) by treatment arm, difference in means with 95% CI, p-value from GEE (repeated measures model), adjusted for baseline central axial length in ITT and PP analysis.
- Uniocular near VA at baseline, meam (SD) by treatment arm in PP analysis.
- Uniocular near VA at months 6, 12 and 18: mean (SD) by treatment arm, difference in means with 95% CI, p-value from GEE (repeated measures model), adjusted for baseline uniocular near VA in ITT and PP analysis.
- Binocular near VA at baseline, mean (SD) by treatment arm in PP analysis.
- Binocular near VA at months 6, 12 and 18: mean (SD) by treatment arm, difference in means with 95% CI, p-value from repeated measures ANCOVA, adjusted for baseline binocular near VA in ITT and PP analysis.
- Pupil diameter at baseline, mean (SD) by treatment arm in PP analysis.
- Pupil diameter at months 6, 12 and 18: mean (SD) by treatment arm, difference in means with 95% CI, p-value from GEE (repeated measures model), adjusted for baseline pupil diameter in ITT and PP analysis.
- Spectacle correction at baseline, no. (%) by treatment arm in PP analysis.
- Spectacle correction at months, 6, 12 and 18: no. (%) by treatment arm, risk difference and p value from repeated measures generalized linear model in ITT and PP analysis.
- Frequency of spectacle correction at baseline (all day and sometimes), no. (%) by treatment arm in PP analysis.
- Frequency of spectacle correction at months 6, 12 and 18 (all day and sometimes): no. (%) by treatment arm in ITT and PP analysis.

- EQ-5D-Y VAS at baseline, mean (SD) by treatment arm in PP analysis.
- EQ-5D-Y VAS at months 6, 12 and 18: mean (SD) by treatment arm, difference in means with 95% CI, p-value from repeated measures ANCOVA, adjusted for baseline EQ-5D-Y VAS in ITT and PP analysis.
- EQ-5D-Y Index score at baseline, mean (SD) by treatment arm in PP analysis.
- EQ-5D-Y Index score at months 6, 12 and 18: mean (SD) by treatment arm, difference in means with 95% CI, p-value from repeated measures ANCOVA, adjusted for baseline EQ-5D-Y Index in ITT and PP analysis.
- Tolerability eye feels at months 6, 12 and 18: mean (SD) by treatment arm, difference in means with 95% CI, p-value from ANOVA, in ITT and PP analysis.
- Tolerability stingy at months 6, 12 and 18: mean (SD) by treatment arm, difference in means with 95% CI, p-value from ANOVA, in ITT and PP analysis.
- Tolerability itchiness at months 6, 12 and 18: mean (SD) by treatment arm, difference in means with 95% CI, p-value from ANOVA, in ITT and PP analysis.
- Tolerability blurry vision at months 6, 12 and 18: mean (SD) by treatment arm, difference in means with 95% CI, p-value from ANOVA, in ITT and PP analysis.
- Tolerability sore eyes at months 6, 12 and 18: mean (SD) by treatment arm, difference in means with 95% CI, p-value from ANOVA, in ITT and PP analysis.
- Tolerability difficult to read/write at months 6, 12 and 18: mean (SD) by treatment arm, difference in means with 95% CI, p-value from ANOVA, in ITT and PP analysis.

8.9 SWAT analyses

Data from medication event monitoring systems (MEMs) are used to measure adherence to medication. For this study, AARDEX software is used to store medication adherence data from MEMs, whilst bottle weight data is measured separately and routinely.

This study within a study (SWAT) will investigate if the inexpensive and pragmatic measure of bottle weight measurements, is as effective as MEMs for measuring compliance to medication in individual patients, and in groups of patients.

For individual patients, MEMs and difference in bottle weight values will be explored, and discrepancies between datasets measured. Summary statistics for differences in bottle weight will be measured according to good (>= 80%), moderate (50% - 79%) and bad (<50%) MEMs adherence. Summary statistics will include mean, min, max, standard deviation, median and interquartile range. Pearson's correlation will be used to measure the relationship between MEMs data and difference in bottle weight data.

Summary statistics including mean and standard deviation will also be calculated for groups of patients. These statistics will be used to examine if bottle weight provides a sufficient approximation of adherence to medication for a group of people in a trial.

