Reaction (SUSAR) product in question set out: - in the case of a product with a marketing authorisation, in the SPC for that product - in the case of any other investigational medicinal product, in the IB relating to the trial in question. Per protocol Population The per protocol population is defined as participants with overall study drug adherence of at least 80% using MEMs data. Intention to treat The intention to treat population is defined as all participants who are		
- in the case of a product with a marketing authorisation, in the SPC for that product - in the case of any other investigational medicinal product, in the IB relating to the trial in question. Per protocol Population The per protocol population is defined as participants with overall study drug adherence of at least 80% using MEMs data. Intention to treat The intention to treat population is defined as all participants who are		
product - in the case of any other investigational medicinal product, in the IB relating to the trial in question. Per protocol Population The per protocol population is defined as participants with overall study drug adherence of at least 80% using MEMs data. Intention to treat The intention to treat population is defined as all participants who are	Reaction (SOSAR)	
- in the case of any other investigational medicinal product, in the IB relating to the trial in question. Per protocol Population The per protocol population is defined as participants with overall study drug adherence of at least 80% using MEMs data. Intention to treat The intention to treat population is defined as all participants who are		
the trial in question. Per protocol Population The per protocol population is defined as participants with overall study drug adherence of at least 80% using MEMs data. Intention to treat The intention to treat population is defined as all participants who are		
Per protocol Population The per protocol population is defined as participants with overall study drug adherence of at least 80% using MEMs data. Intention to treat The intention to treat population is defined as all participants who are		
adherence of at least 80% using MEMs data. Intention to treat The intention to treat population is defined as all participants who are	Per protocol Population	
Intention to treat The intention to treat population is defined as all participants who are	1	
	Intention to treat	

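### The bottle-weight SWAT asks an agreement question, but Pearson's r is its only named comparison statistic, and r cannot show systematic over- or under-statement of adherence

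*Supplement*

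**What the plan says.** SAP section 8.9 sets the SWAT's question: whether bottle weight, as a cheap and practical measure, "is as effective as MEMs for measuring compliance to medication in individual patients, and in groups of patients".

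For individual patients it plans three steps:

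- An exploratory comparison: "MEMs and difference in bottle weight values will be explored, and discrepancies between datasets measured".
- Banded summaries: "Summary statistics for differences in bottle weight will be measured according to good (>= 80%), moderate (50% - 79%) and bad (<50%) MEMs adherence". The statistics are listed: "Summary statistics will include mean, min, max, standard deviation, median and interquartile range".
- Correlation: "Pearson's correlation will be used to measure the relationship between MEMs data and difference in bottle weight data".

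For groups, it plans summary statistics including mean and SD, from which it will judge whether bottle weight approximates adherence well enough for a group in a trial.

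Section 8.9 gives no conversion of weight difference to percent adherence, no agreement statistic, and no numerical standard for equal effectiveness or adequate approximation.

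**The concern.** Whether one measure can stand in for another is a question of agreement: how far apart are the two readings for the same child, and is one of them systematically off? Pearson's r answers a different question, namely how closely the points follow some straight line, whatever its intercept and positive slope. It also rises with the spread of adherence in the sample, so the same measurement error looks better in a more varied group.

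The mismatch matters for what the SWAT concludes. Bottle weight could track MEMS closely and still overstate every child's adherence, for instance if more liquid leaves the bottle per dose than assumed. A high r would be accurate as a statement of association, but it would not support using bottle weight to decide whether a given child reached 80%. The trial itself uses that cut, for its per-protocol definition (section 4) and for the SWAT's good-adherence band.

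**Working it through.** Section 8.9 states no sample size, limit or target, so there is no planned figure to reproduce. The check has three parts.

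**1. What each planned step can show**

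| Step in section 8.9 | Shows | Does not show |
|---|---|---|
| Discrepancies between datasets | Undefined: weight and percent have no common scale | Bias in percent adherence |
| Weight differences by MEMS band | Ordering and overlap of the bands | Bias; how often a weight-based rule misplaces a child |
| Pearson's r | Linear association | Constant or proportional error |
| Group mean and SD | Level and spread of each measure on its own scale | Whether the group means agree |

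**2. Why r is blind to systematic error**

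For bottle weight X, MEMS adherence Y and b > 0, cov(a + bX, Y) = b·cov(X, Y) and SD(a + bX) = b·SD(X). The factor b cancels and a drops out, so r(a + bX, Y) = r(X, Y). This is also why r can be computed on unconverted weights: it ignores scale.

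**3. Size, by simulation**

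These inputs are assumed and are not in the SAP. MEMS adherence is normal with mean 75 and SD 18, with values outside 0 to 100% set to the nearest limit. Weight-based adherence is on the percent scale and equals MEMS plus normal error of SD 5 or 10, then shifted or rescaled. There are 200,000 simulated children.

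| Error SD | Systematic error | r | Mean difference | 95% limits of agreement | Lin's concordance | Same side of 80% |
|---|---|---|---|---|---|---|
| 5 | none | 0.958 | 0.0 | -9.8 to 9.8 | 0.957 | 0.917 |
| 5 | +20 points | 0.958 | 20.0 | 10.2 to 29.8 | 0.568 | 0.600 |
| 5 | ×1.3 | 0.958 | 22.3 | 6.2 to 38.3 | 0.563 | 0.625 |
| 5 | ×0.7 | 0.958 | -22.3 | -34.3 to -10.3 | 0.422 | 0.610 |
| 10 | none | 0.858 | 0.0 | -19.6 to 19.6 | 0.848 | 0.842 |
| 10 | +20 points | 0.858 | 20.0 | 0.4 to 39.6 | 0.527 | 0.618 |
| 10 | ×1.3 | 0.858 | 22.3 | -5.0 to 49.6 | 0.512 | 0.641 |
| 10 | ×0.7 | 0.858 | -22.3 | -39.2 to -5.4 | 0.407 | 0.620 |

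Within each error SD, r does not move, while the agreement measures change sharply.

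**Random scatter alone.** Even with no bias, a respectable r leaves wide uncertainty for one child. With equal SDs on the percent scale, the limits are ±1.96·SD·√(2(1 − r)):

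- SD 20 (assumed): ±24.8 points at r = 0.8 and ±17.5 at r = 0.9.
- SD 10 (assumed): ±12.4 and ±8.8.

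If both measures are bivariate normal with their mean exactly on the cut, the share of children on opposite sides is arccos(r)/π. That is 0.205 at r = 0.8 and 0.144 at r = 0.9. Placing the mean on the cut is the least favourable position for a given r. These scatter figures assume zero bias, so they do not illustrate the systematic error in part 2.

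**The case against.** The strongest reply is that the plan does not rest on correlation. It sets no threshold on r and does not make r a decision rule. It also says discrepancies will be measured, and it gives the minimum, maximum, SD and IQR of weight difference on each side of the 80% MEMS cut. Wide overlap between bands would be visible beside r. This stands: a reader might infer that section 8.9 decides the replacement question by Pearson correlation alone, and the text does not say that. What the other steps lack is a common scale. Overlap in weight units shows that misclassification is possible, but gives neither its rate nor any bias in percent adherence.

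A second reply is that nothing in the trial's inference depends on this. That also stands. A reader might infer from the shared 80% cut that the per-protocol population is at risk. However, section 4 defines that population by "adherence of at least 80% using MEMs data", and bottle weight defines no analysis set.

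A third reply is that an agreement analysis needs an expected drop weight, which the SAP does not give, so correlation with banded summaries is a reasonable start on unconverted data. As a description it is. The protocol, to which the SAP refers for data collection, was not available here and may describe weighing or a conversion. The case therefore rests on the choice of statistic for the stated question more than on the missing conversion.

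**Conclusion.** The point holds in a limited form and is a cheap improvement. The SWAT poses an agreement question, its only named comparison statistic measures association, and its other steps cannot supply bias or misclassification as specified. The invariance of r is exact and needs no assumption. The size is illustrative: under the simulation's assumed inputs, agreement on the 80% class falls from 0.917 to about 0.60–0.63 (error SD 5), or from 0.842 to about 0.62–0.64 (error SD 10), with r unchanged.

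The scatter figures should not be read as a forecast that about 20% or 14% of the trial's children would be misclassified. The documents give no SD, mean or expected r for adherence. Only the SWAT's conclusion about bottle weight is affected.

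**What to change.** Amend section 8.9 as follows:

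- **Common scale.** Convert weight used to implied percent adherence: weight used divided by the expected weight of the prescribed drops over the same interval. State the assumed drop weight and repeat the analysis over a plausible range of it.
- **Individuals.** Report the Bland-Altman mean difference and 95% limits of agreement against MEMS percent. Add sensitivity and specificity of weight-based adherence of at least 80% against MEMS adherence of at least 80%.
- **Groups.** Report the mean difference in percent adherence with its 95% CI.
- **Criterion.** State before the data are examined what bias, limits and classification accuracy would count as adequate.
- **Description.** Keep Pearson's r and the banded summaries, labelled as descriptive.

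The cost is some SAP wording and a little extra analysis, with no new participant data. The drawback is reliance on an assumed drop weight. An error in that figure would itself appear as proportional bias, which is why it should be varied.
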